8. STUDY ENDPOINTS

8.1. Primary endpoint

Phase I / Dose escalation part

Primary objective of the phase I trial is to establish the recommended phase II dose (RP2D), the maximum tolerated dose (MTD) evaluated on the first cycle (D1 to D21), the safety profile, and the Dose Limiting Toxicities (DLT) of trabectedin given in combination with durvalumab.

Definition:

Dose-limiting toxicity (DLT):

A DLT is defined as an AE or laboratory abnormality that fulfills all the criteria below:

- Begins on the first 21 days of treatment.
- Is considered to be at least possibly related to the study treatment.
- Meets one of the criteria below, graded as outlined or according to NCI-CTCAEv4.03 :
 - Any grade-4 toxicity (except for vomiting without maximal symptomatic/prophylactic treatment and if toxicity is transaminitis, but which have to be resolved at Day 21, i.e. return to Baseline or grade 1).
 - Grade-3 non-haematological toxicity lasting > 7days (except for 1rst episode of nausea without maximal symptomatic/ prophylactic treatment and if toxicity is transaminitis, which have to be resolved at Day 21, i.e. return to Baseline or grade 1).
 - Grade-3 hematologic toxicity lasting for > 7days.
 - Grade 4 neutropenia with fever.
 - Grade > 2 thrombocytopenia with bleeding.

Endpoints:

- Toxicity graded using the common toxicity criteria from the NCI-CTCAE v4.03.
- Incidence rate of DLT at each dose level during the first 21 days.

Phase I / Expansion cohorts

Primary objective of the expansion cohorts is to evaluate preliminary signs of the antitumor activity of trabectedin given in combination with durvalumab in terms of objective response under treatment. Following RECIST v1.1 recommendations ([appendix 3](#)):

- Objective response rate (ORR) is defined as the proportion of patients with complete or partial response (CR, PR) as per RECIST v1.1 criteria.
- Objective response under treatment is recorded from study treatment initiation until the end of treatment and determined once all the data for the patient is known.
- Claimed responses will have to be confirmed at least 4 weeks later to ensure responses identified are not the result of measurement errors.
- **Disease status under treatment, whatever the response observed, will be centrally reviewed for all patients, by an independent expert radiologist. Reviewed data will be used for the efficacy analysis.**

8.2. Secondary endpoints

Phase I / Dose escalation part

- Preliminary signs of antitumor activity in terms of:
 - Best overall response is defined as the best response recorded from the start of the study treatment until the end of treatment taking into account any requirement for confirmation as per RECIST v1.1 criteria ([appendix 3](#)):
Following RECIST v1.1 recommendations:
 - The best overall response is determined once all the data for the patient is known.
 - Claimed responses will have to be confirmed at least 4 weeks later to ensure responses identified are not the result of measurement errors.
 - Objective response rate (ORR) is defined as the proportion of patients with complete response or partial response according to RECIST v1.1 criteria ([appendix 3](#)). ORR under treatment and 6-month ORR will be reported. ORR under treatment is recorded from study treatment initiation until the end of treatment. Following RECIST v1.1 recommendations:
 - ORR under treatment is determined once all the data for the patient is known.
 - Claimed responses will have to be confirmed at least 4 weeks later to ensure responses identified are not the result of measurement errors.
 - Progression-free rate (PFR) is defined as the proportion of patients with complete response, partial response or stable disease more than 24 weeks as defined as per RECIST v1.1 criteria ([appendix 3](#)). 6-month PFR will be reported. . Following RECIST v1.1 recommendations, claimed responses will have to be confirmed at least 4 weeks later to ensure responses identified are not the result of measurement errors.
 - Progression-free survival (PFS) is defined as the time from study treatment initiation to the first occurrence of disease progression or death (of any cause), whichever occurs first. 1-year PFS rate will be reported.
 - Overall Survival (OS) is defined as the time from study treatment initiation to death (of any cause). 1-year OS rate will be reported.
- Pharmacodynamic study:
 - Blood samples:
 - Serum level of cytokines, kynurenine and immunophenotyping of circulating immune cells
 - Analyses of circulating DNA for identification and monitoring of mutations observed at the level of the circulating tumor cells (liquid biopsies concept).
 - Tumor samples: Fresh pre-treatment and on-treatment tumor biopsies will be performed. Samples will be formalin fixed and paraffin-embedded or fresh frozen, and will be analyzed for:
 - Hematoxylin and eosin staining (H&E).
 - Immunohistochemistry (IHC) assessments including, but not limited to, the following markers: SP263 SP28-8 (PDL1), CSF-1R, CD68/CD163, CD8, MHC class I/II, CD31 (microvessel density), Ki67 and other exploratory markers. The analysis will be prioritized based on the amount of material available.

- Genomics and transcriptomics exploratory analysis for predictive signatures in responders and mechanisms of resistance in non-responders.

Phase I / Expansion cohorts

- Preliminary signs of antitumor activity in terms of 6-month ORR, best overall response, 6-month PFR, 1-year OS and PFS rates defined as for the escalation part of the phase I trial.
- Toxicity defined above as for the escalation part.
- Pharmacodynamics study defined above as for the escalation part.

9. STATISTICAL CONSIDERATIONS

9.1. Hypotheses and number of subjects needed

9.1.1. Phase I (Dose escalation part)

- 3 dose levels
- A minimum of 3 patients will be entered in each dose level
- A maximum of 6 patients will be entered in each dose level

Therefore, the maximum number of patients is estimated to be 18 patients assessable for safety. To account for patients not assessable, we anticipate accruing a maximum of **20 patients for the dose escalation part of the phase I trial**.

9.1.1. Phase I (Expansion cohorts)

- The primary objective is to determine preliminary signs of anti-tumor activity of trabectedin given in combination with DURVALUMAB among two selected cohorts of patients (STS and ovarian carcinomas) in terms of objective response under treatment as per RECIST v1.1 criteria.
- Once the Maximum Tolerated Dose (MTD) is established for trabectedin, 2 distinct cohorts will be treated at the MTD:
 - Cohort A: patients with advanced STS.
 - Cohort B: patients with advanced ovarian carcinomas
- For each cohort:
 - Sample size is calculated based on the first stage of a 2-stage Gehan design assuming a 20% efficacy rate, 5% false positive rate and 10% precision (Gehan 1961).
 - 14 eligible and assessable subjects are required.
 - If at least one objective response (CR or PR as per RECIST v1.1) is observed under treatment, the study drug association will be considered worthy of further testing in this indication.

Assuming 10% patients not eligible or that cannot be assessed for the primary endpoint, **15 patients will be recruited for each of the 2 cohorts**, i.e. a total of **30 patients will be included in the expansion cohorts**.

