Statistical considerations	
SAMPLE SIZE CONSIDERATIONS
 
Phase I (Dose escalation part):
 
 • 3 dose levels • A minimum of 3 patients and a maximum of 6 patients per dose level • Therefore, the maximum number of patients is estimated to be 18 patients assessable for safety. To account for patients not assessable, we anticipate accruing a maximum of 20 patients for the dose escalation part of the phase I trial.

Phase I (Expansion cohorts):

- The primary objective is to determine preliminary signs of anti-tumor activity of trabectedin given in combination with Durvalumab among two selected cohorts of patients (STS and ovarian carcinomas) in terms of objective response rate (ORR) under treatment as per RECIST v1.1 criteria.
- Once the MTD is established for trabectedin, 2 distinct cohorts will be treated at the MTD:
 - Cohort A: patients with advanced STS.
 - Cohort B: patients with advanced ovarian carcinomas
- For each cohort:
 - Sample size is calculated based on the first stage of a 2-stage Gehan design assuming a 20% efficacy rate, 5% false positive rate and 10% precision (Gehan 1961).
 - 14 eligible and assessable subjects are required.
 - If at least one objective response (CR or PR as per RECIST v1.1) is observed under treatment, the study drug association will be considered worthy of further testing in this indication.
 - Assuming, 10% are not eligible or cannot be assessed for the primary endpoint, **15 patients will be recruited for each of the 2 cohorts**, i.e. a total of 30 patients will be included in the expansion cohorts.

STATISTICAL ANALYSIS

- All analyses for the dose escalation part trial and the expansion cohorts will be descriptive; no p-values will be calculated.
- For the dose escalation part:
 - Data analyses will be provided by dose groups and for all study patients, combined wherever appropriate.
 - Toxicity observed at each dose level, graded according to the common toxicity criteria from the NCI-CTCAE v4.03, will be recorded in terms of event type, severity, dates of beginning and end, reversibility and evolution. Data will be gathered in tables summarizing toxicities and side effects for each dose level and cycle.
 - DLT will be described in terms of number and incidence rates at each dose level. The number and percentage of patients who will have developed a DLT in each dose level will also be reported.

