9.3.2.2. EXPANSION COHORTS

- All analyses will be descriptive; no p-values will be calculated.
- Analyses will be conducted separately for sarcoma and ovarian cancer patients.
- Primary efficacy endpoint will be analysed based on the eligible and assessable population (see [chapter 10.2](#) for definition):
 - Each patient will be assigned one of the following categories:
 - Complete response
 - Partial response
 - Stable disease
 - Progression
 - Inevaluable for response
 - The rate of objective response (complete or partial response) under treatment will be reported:
 - All eligible and assessable patients ([section 10.2](#)) will be included in the denominator for the calculation of the objective response rate (ORR).
 - The 95% two-sided confidence limits will be provided for the ORR (binomial law).
 - First endpoint conclusions will be based on the objective response rate ORR for all eligible and assessable patients ([section 10.2](#)) after centralized radiological review of the data.
- As regards to the other efficacy endpoints, the analyses will be carried out in the eligible and assessable population:
 - Each patient will be assigned one of the following categories:
 - Complete response
 - Partial response
 - Stable disease
 - Progression
 - Inevaluable for response
 - The rate of best overall response will be calculated as the number of patients alive with the best response (recorded from the start of the treatment) divided by the number of patients eligible and assessable ([section 10.2](#)).
 - The 6-month progression-free rate will be calculated as the number of patients remaining alive and progression-free at 6 months from the start of the treatment divided by the number of patients eligible and assessable ([section 10.2](#)).
 - The 6-month objective response rate will be calculated as the number of patients alive with complete or partial response at 6 months divided by the number of patients eligible and assessable ([section 10.2](#)).
 - The 95% two-sided confidence limits will be provided for the calculated rates (binomial law)
- The safety analysis will be performed on the safety population.
- Quantitative variables will be described using mean and standard deviations if the normality assumption is satisfied, else other descriptive statistics (median, range, quartiles) will be reported.
- Qualitative variables will be described using frequency, percentage and 95% confidence interval (binomial law).

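### The 5% behind the 14 patients per expansion cohort is a false-negative rate at ORR 20%, not the false-positive rate the plan calls it

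*Protocol*

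**What the plan says.** Protocol 9.1.1, Phase I (Expansion cohorts), sizes each of the two cohorts (STS and ovarian carcinoma) from the first stage of a "2-stage Gehan design assuming a 20% efficacy rate, 5% false positive rate and 10% precision". It then states that "14 eligible and assessable subjects are required". The decision rule follows directly: if one or more complete or partial responses are seen under treatment, "the study drug association will be considered worthy of further testing in this indication". The same design statement, number and rule appear under Statistical considerations in the Protocol synopsis and in the SAP synopsis.

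Two further statements bear on how much the label matters. The synopses say that "All analyses for the dose escalation part trial and the expansion cohorts will be descriptive; no p-values will be calculated". Protocol 9.3.2.2 and SAP 3.2.2 plan a two-sided 95% binomial confidence interval for the ORR.

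Neither document gives an ORR that would be considered uninteresting, and neither describes the 5% as anything other than a false-positive rate.

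**The concern.** In this plan a positive result is defined by the go rule: the combination is judged worth testing further in that indication. A false positive is therefore a go for a combination that is not active enough to deserve one. A 5% false-positive rate tells the reader that such a go would be rare.

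A rule that needs only one response among 14 patients cannot have that property unless the uninteresting response rate is almost zero. The protocol's own background makes that unlikely. Section 1.1 describes response rates with the agents approved for pretreated STS, trabectedin among them, as low, and section 1.3.3 mentions objective responses on single-agent trabectedin. If durvalumab added nothing, some responses could still be expected from trabectedin.

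This is the only go rule for the expansion cohorts' primary endpoint, and it is applied separately in each cohort. A steering committee or later reader who trusts the 5% would take a single response in 14 as much stronger evidence of activity than it is.

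**Working it through.** **Inputs, all from Protocol 9.1.1 (Expansion cohorts):** target ORR 20%; error rate 5%; required n = 14; go if at least 1 of 14 responds. No null ORR is given.

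**1. Reproduce the plan's n.** The chance of no response in n patients at ORR 20% is 0.8^n. Setting 0.8^n ≤ 0.05 gives n ≥ ln(0.05)/ln(0.8) = 13.43, so n = 14.

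- 0.8^13 = 0.0550, above 5%
- 0.8^14 = 0.0440, below 5%

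This is the stated 14 exactly. The 5% has been used as P(no response | ORR = 20%), the chance of missing a combination that reaches the target. The matching chance of a go is 1 − 0.0440 = 0.956. Equivalently, 0/14 has a one-sided 95% upper limit of 1 − 0.05^(1/14) = 19.3%, just under the 20% target.

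**2. Try the 5% as a false-positive rate.** Under the stated rule, P(go | p) = 1 − (1 − p)^n. This rises with n, so a 5% limit on it at a null rate p sets a maximum n, not a minimum: n ≤ ln(0.95)/ln(1 − p).

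- assumed null ORR 1%: 5.10, so at most 5 patients
- assumed null ORR 2%: 2.54, so at most 2 patients
- assumed null ORR 5%: 1 patient

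A false-positive limit therefore cannot lead to a requirement of 14 patients under this rule.

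**3. Find where the rule does have a 5% false-positive rate.** With n = 14, solve 1 − (1 − p)^14 = 0.05: p = 1 − 0.95^(1/14) = 0.00366, or 0.37%.

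**4. Chance of a go with 14 patients.** The ORRs below 20% are assumed for illustration, since the documents give none.

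| True ORR | P(at least 1 response in 14) |
|---|---|
| 0.37% | 5% |
| 1% | 13.1% |
| 2% | 24.6% |
| 5% | 51.2% |
| 10% | 77.1% |
| 20% | 95.6% |

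**5. Would another cut-off explain the label?** Requiring at least 2 responses in 14 would hold false positives at 5% up to a null ORR of 2.6%, with an 80.2% chance of a go at ORR 20%. The plan does not use that rule.

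**6. Secondary: the 10% precision.** The standard error at ORR 20% with 14 patients is √(0.2 × 0.8/14) = 0.107, or 10.7 points. A standard error of 10 points would need 0.16/0.01 = 16 patients, and a 95% half-width of 10 points would need 1.96² × 0.16/0.01 = 61.5, so 62. The precision figure is undefined and plays no part in the 14.

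**The case against.** The strongest defence is that this is a label and not a miscalculation. The number 14 reproduces exactly, and nothing computed in the trial uses the 5%. There is also a reading under which the term is defensible: if the hypothesis to be rejected is that the ORR is at least 20%, then rejecting it wrongly after 0/14 is a type I error of 4.4%.

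The consequences are also modest. The aim is preliminary signs of activity. The recommended phase II dose is chosen on safety and pharmacodynamic data (Protocol 3.2 and 3.4). No p-values are planned. For the weakest possible go, 1/14, the exact 95% interval runs from 0.2% to 33.9%, so the thinness of the evidence would be visible. Finally, a go at 5% or 10% is an error only if those rates are uninteresting, which the plan does not say.

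Much of this stands. The sample size is right, the harm is limited, and the probabilities at 1% to 10% depend on assumed rates. The alternative hypothesis does not rescue the label: it appears in neither document, and it would make a no-go the positive result when the plan attaches the positive conclusion to a go. The confidence interval does not settle the matter either, because the rule turns on one response and not on the interval. The point about precision is fair: an input that belongs to the two-stage design but goes unused in the first stage is unclear rather than wrong.

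**Conclusion.** The concern holds. The 5% that yields 14 patients is a false-negative rate, 4.4% at a true ORR of 20%. The false-positive rate claimed for the go rule applies only at a true ORR of 0.37%, and it exceeds 5% for any uninteresting ORR above that.

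The first conclusion uses only the plan's own target rate, sample size and rule. How far the false-positive rate exceeds 5% in practice depends on an uninteresting ORR that the documents do not give: 13% if it were 1%, 51% if it were 5%.

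This is an error in a stated operating characteristic, not in the sample size, and it should be corrected because it appears in both documents and describes the only go rule on the expansion primary endpoint. The 10% precision is a minor point of clarity that would not merit a comment alone.

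**What to change.** In Protocol 9.1.1 (Expansion cohorts), the Protocol synopsis and the SAP synopsis:

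1. Replace the false-positive label with: *5% false-negative rate (4.4% with 14 patients at a true ORR of 20%)*.
2. Add one sentence saying that the first-stage rule of at least one response does not control the false-positive rate. Preferably give the chance of a go at a few true ORRs marked as illustrative (13% at 1%, 25% at 2%, 51% at 5%, 77% at 10%). Naming an uninteresting ORR for each cohort would be helpful but is optional.
3. As a secondary clarification, delete the 10% precision, or define it and give the first-stage standard error of 10.7 points at ORR 20%.

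The cost is wording in two places in the protocol and one in the SAP. The 14 patients, the go rule, the estimator and the planned interval do not change. The only drawback for the sponsor is that the stated properties of the rule look less favourable.

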I acknowledge having read the whole protocol, and I pledge to lead this protocol in accordance with the Good Clinical Practice (decision of 24 November 2006), the Public Health Law No. 2006-806 of August 09, 2004 and the implementing Decree n° 2006-477 of April 26, 2006 and as described in this document.

I assume my responsibilities as referent investigator including:

- Collection of informed consent, dated and signed by patients before any selection procedure in the protocol,
- Validation of case report forms, completed for each patient included in the study,
- Direct access to source documents for verification by the clinical research assistant (CRA) commissioned by the sponsor,
- Archiving of critical documents of the study for a 15 year-period.

Name and address of the hospital

Name of the Coordinating Investigator :

Date : |__|__| |__|__| |__|__| |__|

Signature :

SYNOPSIS

Title of the study	Trabectedin combined with durvalumab (MEDI4736) in patients with advanced pretreated soft-tissue sarcomas and ovarian carcinomas. A Phase Ib study
Abbreviation of the trial	TRAMUNE
Sponsor Identification	Institut Bergonié, Regional Comprehensive Cancer Center
Coordinating Investigator	Doctor [name] Department of Medical Oncology
Scientific responsive	Doctor [name] Department of Medical Oncology
Number of investigational sites planned	
Phase I (dose escalation): 2 centers - Institut Bergonié, Bordeaux, France (PI : Pr [name]) - Centre Léon Bérard, Lyon, France (PI : [name])
 
Phase I (expansion cohorts): 3 centers - Institut Bergonié (PI : Pr [name]) - Centre Léon Bérard (PI : [name]) - Institut Gustave Roussy, Villejuif, France (PI : [name] [name])

Number of patients	
Phase I (Dose escalation): 20 patients
 
Phase I (Expansion cohorts): 30 patients (15 patients STS/15 patients ovarian carcinomas)

Duration of the study	
Planned enrollment period: 30 months
 
Treatment duration: until progression
 
Follow-up: 1 year
 
Study period: 3 years

Medical conditions	
Adult patients with:
 
 - locally advanced or metastatic soft-tissue sarcoma (STS) who have failed anthracycline-containing chemotherapy (CT), - or ovarian carcinoma, without known g/s BRCA mutation, and must have received at least one line of platinum-containing regimen.

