9.2.2. Phase I (Expansion cohorts)

- Eligible population: All patients included without major violation of eligibility criteria.

- Population assessable for efficacy: All patients eligible and for whom the following conditions are satisfied:
 - Received at least one complete or two incomplete treatment cycles,
 - At least one disease measurement recorded not less than six weeks after treatment onset.
- The following patients will also be included in the population assessable for efficacy; they will be considered as "inevaluable for response" for the primary endpoint as per RECIST v1.1 criteria (i.e. objective response under treatment) and not be replaced in the primary efficacy analysis:
 - Any eligible patients who received at least one treatment cycle or two incomplete treatment cycles and experience disease progression or die due to disease progression prior to response evaluation (will be considered as "inevaluable for response" due to early progression).
 - Patients withdrawn due to drug-related toxicity without any tumor assessments after the start of study treatment (will be considered as "inevaluable for response" due to toxicity).
 - Patients who received at least one administration of the treatment AND withdrawn due to significant clinical deterioration of unknown reason AND without any tumor assessments after the start of study treatment (will be considered as "inevaluable for response" due to significant clinical deterioration).
- Safety population: all patients having received at least one (any) treatment administration.

Patient's replacement:

- Any patient not eligible or not assessable for efficacy will be replaced.
- However, any patient who received at least one administration of the study drug will be included in the safety analysis.

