	
(ORR) under treatment as per RECIST v1.1 criteria.
 
 Once the MTD is established for trabectedin, 2 distinct cohorts will be treated at the MTD: 
 Cohort A: patients with advanced STS. Cohort B: patients with advanced ovarian carcinomas For each cohort: 
 Sample size is calculated based on the first stage of a 2-stage Gehan design assuming a 20% efficacy rate, 5% false positive rate and 10% precision (Gehan 1961). 14 eligible and assessable subjects are required. If at least one objective response (CR or PR as per RECIST v1.1) is observed under treatment, the study drug association will be considered worthy of further testing in this indication. Assuming, 10% are not eligible or cannot be assessed for the primary endpoint, 15 patients will be recruited for each of the 2 cohorts, i.e. a total of 30 patients will be included in the expansion cohorts. 
STATISTICAL ANALYSIS
 
 All analyses for the dose escalation part trial and the expansion cohorts will be descriptive; no p-values will be calculated. For the dose escalation part: 
 Data analyses will be provided by dose groups and for all study patients, combined wherever appropriate. Toxicity observed at each dose level, graded according to the common toxicity criteria from the NCI-CTCAE v4.03, will be recorded in terms of event type, severity, dates of beginning and end, reversibility and evolution. Data will be gathered in tables summarizing toxicities and side effects for each dose level and cycle. DLT will be described in terms of number and incidence rates at each dose level. The number and percentage of patients who will have developed a DLT in each dose level will also be reported. Categorical endpoints (e.g. response) will be reported in terms of counts by dose level. For the expansion cohorts: 
 Categorical endpoints will be reported in terms of counts and proportions. Objective response rate under treatment, best response rate, 6-month PFR and 6-month ORR rates will be estimated using binomial estimates and reported with their 95% confidence interval (CI). Continuous endpoints will be reported in terms of summary statistics that will include number of patients, median, minimum, and maximum, and additional percentiles if appropriate. Survival endpoints (PFS and OS) will be analyzed using the Kaplan-Meier method. The median survival rates will be reported with a 95% confidence interval. Median follow-up will be calculated using the reverse Kaplan-Meier method. We will describe also the observed median follow-up.

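### Recruiting 15 per expansion cohort allows for one lost patient (6.7%), not the stated 10%, so the total of 30 is understated (minor)

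*Protocol*

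**What the plan says.** Protocol 9.1.1 (Expansion cohorts) bases each cohort on the first stage of a Gehan design with a "20% efficacy rate, 5% false positive rate and 10% precision". The combination is judged worth further testing on this condition: "If at least one objective response (CR or PR as per RECIST v1.1) is observed under treatment". The required number, given in the same words in the protocol and in the SAP synopsis, is "14 eligible and assessable subjects are required".

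The step from required to recruited patients begins "Assuming 10% patients not eligible or that cannot be assessed for the primary endpoint" and concludes that "15 patients will be recruited for each of the 2 cohorts", so that "30 patients will be included in the expansion cohorts". The sample-size text of both synopses repeats these figures. The number-of-patients row of both synopses gives "30 patients (15 patients STS/15 patients ovarian carcinomas".

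Elsewhere, Protocol 9.2.2 states: "Any patient not eligible or not assessable for efficacy will be replaced". SAP 2.1.2 has the same rule. Both sections keep some patients without an evaluable response in the assessable population and do not replace them: those with early progression, withdrawal for drug-related toxicity, or clinical deterioration. These patients are not part of the 10%.

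**The concern.** Three figures stand side by side in one short passage: 14 required, 10% lost, 15 recruited. The third does not follow from the first two under either usual way of allowing for losses. A reader who checks the sum finds that 15 patients carry a smaller allowance than the text claims.

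At stake is the stated size of the expansion part. The plan both inflates for losses and replaces every loss, and does not say how the two combine. The sample-size text does not mention replacement. Protocol 3.5, on replacement, sends the reader to section 10.2, which holds the adverse-event definitions, while the rule is in 9.2.2. From the sample-size text alone it is unclear whether 15 is a target, a ceiling or a starting number.

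**Working it through.** **Inputs.** Response rate of interest 20%, error 5%, rule of at least one response, 14 assessable, 10% loss, 15 per cohort, 30 in total (Protocol 9.1.1, Expansion cohorts); replacement of all ineligible or non-assessable patients (Protocol 9.2.2, SAP 2.1.2).

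**1. The 14 reproduces.** The first stage takes the smallest n for which the chance of no response at a true 20% rate is at most 5%, that is (1 − 0.20)^n ≤ 0.05.
- n = 13: 0.8^13 = 0.0550, too high.
- n = 14: 0.8^14 = 0.0440, which meets it.

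The 5% reproduces 14 only as the risk of missing a 20% response rate, although the text labels it a false positive rate. That is a separate matter of labelling.

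**2. The 15 does not follow from 10%.**
- Dividing by the retained fraction: 14/(1 − 0.10) = 15.56, rounded up to 16.
- Adding 10%: 14 × 1.10 = 15.4, rounded up to 16.
- Expected assessable from 15: 15 × 0.90 = 13.5, below 14.
- Expected assessable from 16: 16 × 0.90 = 14.4.
- Loss that 15 can absorb: 1 − 14/15 = 6.7%, one patient.

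Fifteen results only from rounding 15.56 or 15.4 down.

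**3. Enrolment once losses are replaced.** Assume that each patient is lost independently with probability 0.10 and that each cohort stops when it has 14 assessable patients.
- Mean per cohort: 14/0.9 = 15.56. Mean for both: 28/0.9 = 31.1.
- More than 30 are needed when the first 30 patients of the combined sequence yield fewer than 28 assessable, that is at least 3 losses in 30.
- P(0 losses) = 0.9^30 = 0.042.
- P(1 loss) = 30 × 0.1 × 0.9^29 = 0.141.
- P(2 losses) = 435 × 0.01 × 0.9^28 = 0.228.
- P(more than 30) = 1 − (0.042 + 0.141 + 0.228) = 0.589, about 59%.

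If 15 are instead recruited in each cohort first and shortfalls are then replaced, the total exceeds 30 whenever either cohort has two or more losses. P(at least 14 of 15 assessable) = 0.9^15 + 15 × 0.1 × 0.9^14 = 0.549, so the probability is 1 − 0.549² = 0.70.

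**The case against.** The strongest reply is that 14 assessable patients is the binding requirement and 15 only a recruitment forecast. The replacement rule covers the same two categories as the 10% allowance, so a second loss in a cohort is made good. The gap is one patient per cohort, and the expected excess is about one patient over both. The documents do not state which formula or rounding was used. The escalation part calls its 20 a maximum, whereas the expansion text does not call 30 a ceiling. Moreover, 16 would not secure 14 without replacement either: P(at least 14 of 16 assessable) at 10% loss is 79%.

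Most of this stands. It disposes of a stronger reading that a reader might infer: that each cohort would fall short of 14 with probability 1 − 0.549 = 45%, or that the risk of missing a 20% response rate would rise to 5.5%, as it does with 13 patients. Both figures hold only if replacement is ignored, and the documents provide for replacement.

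The reply does not rescue the stated allowance. Both usual formulas exceed 15, and a minimum requirement calls for rounding up. Nor does it make the total right, since replacement moves the discrepancy from assessable patients to patients enrolled.

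**Conclusion.** The point holds as an error in the recruitment number and total, of minor severity. Fifteen per cohort carries an allowance of 6.7%, not 10%; the figures that match 10% are 16 and 32. The required 14, the decision rule and its 4.4% risk are unaffected provided replacement continues until 14 are assessable. On the plan's own loss rate the total of 30 is more likely than not to be exceeded: about 31 patients on average, and more than 30 with probability of about 59% (70% if 15 are recruited first in each cohort). These results assume independent losses at exactly 10% in both cohorts. The documents do not support a conclusion that the cohorts are undersized or that 30 is a fixed cap.

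**What to change.** Amend the expansion sample-size text in Protocol 9.1.1 and in both synopses, and align the number-of-patients row in both synopses. Either of two wordings would do:

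- Fifteen per cohort allows for one non-assessable patient (about 7%); further losses are replaced until 14 are assessable, so total enrolment may exceed 30.
- Sixteen per cohort, 32 in total, allows for 10% not eligible or not assessable; losses beyond that are replaced until 14 are assessable.

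The replacement sentence is needed with either, because 16 alone does not guarantee 14. The cross-reference in Protocol 3.5 should point to 9.2.2 at the same time. The cost is a few sentences of text. No procedure, endpoint, population or analysis changes; the second wording raises the stated enrolment by two.
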